8. SAFETY REPORTING

Adverse events and device deficiencies, noted by study staff and reported by the subject, and occurring from the time of study device implantation through to study completion should be recorded on the appropriate CRFs and reported as below.

8.1. Definitions for safety reporting

A. Adverse Event (AE)

An AE is any untoward medical occurrence, unintended disease or injury, or untoward clinical signs (including abnormal laboratory findings) in subjects, users or other persons, whether or not related to the investigational medical device [8].

This definition includes:

- events related to the investigational medical device or the comparator
- events related to the procedures involved
- a worsening of any conditions previously recorded as part of the medical history assessment

For users or other persons, this definition is restricted to events related to investigational medical devices.

B. Serious Adverse Event (SAE)

A SAE is an adverse event that [8]:

- led to death,
- led to serious deterioration in the health of the subject, that either resulted in:
 - 1) a life-threatening illness or injury, or
 - 2) a permanent impairment of a body structure or a body function, or
 - 3) in-patient or prolonged hospitalization, or
 - 4) medical or surgical intervention to prevent life-threatening illness or injury or permanent impairment to a body structure or a body function
- led to foetal distress, foetal death or a congenital abnormality or birth defect

Planned hospitalization for a pre-existing condition, or a procedure required by the protocol, without serious deterioration in health, is not considered a serious adverse event.

C. Adverse Device Effect (ADE)

An ADE is an adverse event related to the use of an investigational medical device [8].

This definition includes:

- adverse events resulting from insufficient or inadequate instructions for use, deployment, implantation, installation, or operation, or any malfunction of the investigational medical device
- any event resulting from use error or from intentional misuse of the investigational medical device.

D. Serious Adverse Device Effect (SADE)

An SADE is an adverse device effect that has resulted in any of the consequences characteristic of a serious adverse event [8].

E. Unanticipated Serious Adverse Device Effect (USADE)

A serious adverse device effect which by its nature, incidence, severity or outcome has not been identified in the current version of the risk analysis report or the clinical investigation plan [8, 9].

F. Device Deficiency

A device deficiency is an inadequacy of a medical device with respect to its identity, quality, durability, reliability, safety or performance. Device deficiencies include malfunctions, use errors, and inadequate labelling.

For the purpose of this study, device deficiencies should be reported when they concern any component of the study device as well as its packaging and tools that need to be used during implantation according to the Instructions for Use.

8.2. Safety: Investigator's Responsibilities

Investigators shall record AEs and DDs, together with an assessment, in the subject's source data. Following, Investigators are responsible for documenting AEs and DDs on the appropriate CRF and submitting them to the Sponsor according to the timelines described below.

AEs must be recorded in standard English medical terminology.

Unresolved AEs should be followed by the Investigator until the events are resolved, the subject is lost to follow-up or through to the end of the study, whichever timing occurs first. Unresolved AEs at the end of the subject's participation will be monitored by the Investigator as part of the site's normal standard of care.

The Investigator will categorize AEs as mild, moderate or severe based on the following definitions:

- Mild: the subject is aware of the sign or symptom, but finds it easily tolerated. The event is of little concern to the subject and/or little clinical significance. The event is not expected to have any effect on the subject's overall health or wellbeing.
- Moderate: the subject has discomfort enough to cause interference with or change in usual activities. The event is of some concern to the subject's health or wellbeing and may require medical intervention and/or close follow-up.
- Severe: the adverse event interferes considerably with the subject's usual activities. The event is of definite concern to the subject and/or poses substantial risk to the subject's health or wellbeing. The event is likely to require medical intervention and/or close follow-up and may be incapacitating or life threatening. Hospitalization and treatment may be required.

The Investigator is responsible for describing the relationship of the AE to the study device/procedure based on the following definitions:

- Unrelated: the event is clearly not related to the study device or procedure
- Possible: the event may or may not be related to the study device or procedure. A relationship cannot be ruled out.
- Definite: the event is clearly related to the study device or procedure.

8.3. Timelines for Submission of Safety Information:

The timelines begin when the Investigator becomes aware of the event.

The Investigator will report to the Sponsor:

- As soon as possible, but no greater than 24 hours upon becoming aware of the event:
 - SAEs
 - SADEs
 - USADEs
 - DDs that could have led to a SADE:
 - if suitable action had not been taken
 - if intervention had not been made, or
 - if circumstances had been less fortunate
 - Re-operation at the study site. Sponsor will provide an explant retrieval kit on becoming aware of a revision and ask the Investigator to return any revised components for retrieval analysis.

Investigators may also be asked to supply the Sponsor, upon Sponsor's request, with any additional information related to the safety reporting of a particular event.

The PI will be responsible for reporting to the EC of the study site and to the regulatory authorities, SAEs, SADEs and DDs that could have led to a SADE, as required by the national regulations.

8.4. Safety reporting: Sponsor's Responsibilities

Sponsor will provide progress reports on safety events to the Investigator to report to the EC as required.

In the case of multicenter studies, Sponsor will inform all Investigators in writing of all SAEs that were reported by all sites throughout the clinical investigation and based on perceived risk.

The Sponsor will also, in case of SADEs and DDs that could have led to SADEs, determine whether the risk analysis needs to be updated and assess whether corrective or preventive action is required.

9. STATISTICAL PROCEDURES

9.1. Hypothesis and Sample size calculation

The following hypotheses will be tested:

H_0 : The null hypothesis is that there is no mean difference between the position of the last trial rasp and the final implant position of the SL-PLUS® MIA Ti/AH femoral hip stem.

H_1 : The alternative hypothesis is that there is a mean difference between the position of the last trial rasp and the final implant position of the SL-PLUS® MIA Ti/AH femoral hip stem.

The study hypothesis can be written as:

$$H_0: \mu=0 \text{ vs. } H_1: \mu \neq 0$$

In 2007, a non-published cadaver test was performed to measure the difference D between the position of the last trial rasp and the implant position of the SL-PLUS® MIA Ti/AH femoral hip stem. A total of 4 femoral hip stems were implanted into the cadaveric femur. The range of the measured difference was found to be between 0mm and 6mm. However, it is most likely that the maximum difference will be greater 6mm when more cases are studied. To compensate for the small number of evaluated cases, the anticipated variation in D will be extended to 10mm with an estimated standard deviation of 2.5mm. A correlation ρ between the distances x_1 and x_2 is certainly positive but it is unknown how strong the correlation is. The standard deviation sd of the difference D has the following relationship with the standard deviations sd_1 and sd_2 for distances x_1 and x_2 :

$$sd^2 = sd_1^2 + sd_2^2 - 2\rho sd_1 sd_2$$

Since $\rho > 0$ and assuming that $\rho = 0$ will lead to a larger sd and therefore a larger sample size. If assumed that $sd_1 = sd_2$, then $sd^2 = 2sd_1^2$. So assuming sd_1 and sd_2 being equal, the sd will also lead to a larger sample size. Therefore, assuming that the correlation is zero and allowing for both standard deviations sd_1 and sd_2 to be 2.5mm is a conservative approach for computing sample size.

According to orthopaedic surgeons, the maximum difference between the position of the rasp and implant without clinical significance is considered to be 2mm. The standard deviations of sd_1 and sd_2 are estimated as approximately 2.5mm estimated based on the assumptions above and data for the range of difference..

The sample size calculation is based on a two-sided test. The significance level and power of the study are chosen to be 0.05 and 0.90; the minimum mean difference Δ is identified as 2 mm; the standard deviations sd_1 and sd_2 are 2.5mm; the correlation between x_1 and x_2 is set to 0. The following formula can be used to calculate the sample size:

$$N \geq \frac{2(T_{N-1,\alpha/2} + T_{N-1,\beta})^2 sd^2}{\Delta^2}$$

The SAS POWER procedure is used to compute the sample size and at least 35 subjects are needed for the study.

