2.1. Primary Endpoint

The primary endpoint is the mean difference D between the position of the last trial rasp and the final implant position of the SL-PLUS® MIA Ti/HA femoral hip stem. The difference D is determined by analyzing standardized fluoroscopic images taken during surgery.

The difference D is given in mm and is defined as $D = x_1 - x_2$ with x_1 being the distance between the shoulder of the trial rasp and the tip of the greater trochanter and x_2 being the distance between the shoulder of the implant and the tip of the greater trochanter.

The distance to be measured is shown in Figure 1: Example of pre-operative planning.

Figure 1 Pre-operative planning: x = distance between shoulder of implant and the tip of the greater trochanter [mm]

The diameter of the trial head and the final ball head will be measured to calibrate the size of the digital image.

The study hypothesis is defined as:

H_0 : The null hypothesis is that there is no mean difference between the position of the last trial rasp and the final implant position of the SL-PLUS® MIA Ti/AH femoral hip stem.

H_1 : The alternative hypothesis is that there is a mean difference between the position of the last trial rasp and the final implant position of the SL-PLUS® MIA Ti/AH femoral hip stem.

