6.1.2. Assessment 2: Surgery

During surgery two fluoroscopic AP images will be taken showing the position of the final trial rasp with trial head and the final position of the implanted stem with final ball head. The joint will be reduced at the time the images are taken. The AP view should include the full articulation of the operated side with the greater trochanter and the shoulder of the implant / rasp visible.

The images will be de-identified and submitted to an assigned medical person for centralized analysis after surgery. The medical person will be assigned by S&N to analyze the fluoroscopic images and to collect the following information on the appropriate CRF:

- distance x_1 between the shoulder of the trial rasp and the tip of the greater trochanter
- distance x_2 between the shoulder of the implant and the tip of the greater trochanter
- diameter of trial head and final ball head

In addition, the following data will be collected during surgery and recorded on the appropriate CRF:

- It will be recorded what type of rasping instrument was used for femoral preparation giving the following options:
 - Slap hammer
 - Woodpecker
 - Mallet
 - Combination
- Information of implanted devices will be recorded on the CRF and by collecting the chart sticks on the CRF.
- The type of the surgical approach will be collected.
- During surgery it will be recorded if the surgeon needed to correct the position of the stem compared to the final rasp and which one of the following methods was used:
 - Smaller ball head length
 - Larger ball head length
 - Removal of stem and enlargement of femoral bed with last trial rasp
 - Other methods

All intraoperative complications will be recorded as outlined in section 8 Safety reporting.

The leg length difference will be measured by the Investigator or designee peri-operatively shortly after surgery before transfer of the subject to the general ward. The length of each lower extremity is determined in cm by measuring the distance between the ASIS and the medial malleolus by using a measuring tape with the subject in supine position. Measured distances will be recorded on the appropriate CRF.

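### Is the sample size of 40 too small because its planning SD rests on four cadaver values?

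*Protocol*

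**What the plan says.** Protocol 9.1, repeated in SAP 6.3, takes its variability from one unpublished 2007 cadaver test: "A total of 4 femoral hip stems were implanted into the cadaveric femur", with D ranging from 0 to 6 mm. The adjustment for this thin evidence is introduced by "To compensate for the small number of evaluated cases", and it is that "the anticipated variation in D will be extended to 10mm with an estimated standard deviation of 2.5mm".

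The plan then moves from the SD of D to the SDs of the two distances x1 (rasp) and x2 (implant). Their correlation "is certainly positive but it is unknown how strong the correlation is". The calculation takes the case of no correlation: "the standard deviations sd_1 and sd_2 are 2.5mm; the correlation between x_1 and x_2 is set to 0". The resulting judgement is that "allowing for both standard deviations sd_1 and sd_2 to be 2.5mm is a conservative approach for computing sample size".

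With a two-sided 5% test, 90% power and a 2 mm difference, the plan reports 35 evaluable cases. Protocol 9.3 raises this to 40 for 12% missing data. SAP 7.3 plans no interim analysis, and neither document provides for rechecking the SD.

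**The concern.** An SD from four observations has three degrees of freedom and is very imprecise, so calling the plan conservative invites challenge. Three features sharpen the doubt.

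- The 2.5 mm sits near the bottom of the sample SDs that four values spanning 0 to 6 mm can have, so by itself it compensates for little.
- The rise to 3.54 mm comes from assigning an SD of D to x1 and x2 at zero correlation. The documents give no data on the spread of x1 or x2. By the plan's own variance identity, SD(D) passes 3.54 mm once sd_1 exceeds 2.5/sqrt(1 - rho), which is 3.54 mm at rho = 0.5 and 5.59 mm at rho = 0.8.
- The study may add variation that the pilot description does not mention. There are up to four sites. Several rasping methods are allowed ("It will be recorded what type of rasping instrument was used for femoral preparation giving the following options"). Two fluoroscopic images must be scaled ("The diameter of the trial head and the final ball head will be measured to calibrate the size of the digital image").

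At stake is power. Protocol 9.2.1 rejects or retains the null hypothesis on the p value. If the true SD were well above 3.54 mm, a mean shift of 2 mm, the largest difference the plan regards as clinically unimportant, could go undetected and a reader might conclude that rasp and stem agree.

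**Working it through.** **Inputs** (Protocol 9.1 and 9.3): two-sided alpha 0.05, power 0.90, difference 2 mm, sd_1 = sd_2 = 2.5 mm, rho = 0, 12% missing; pilot n = 4, D from 0 to 6 mm.

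**1. The plan's figure.** SD(D) = sqrt(2.5² + 2.5²) = sqrt(12.5) = 3.54 mm. For a paired t-test with N = 35 the noncentrality is (2/3.536) × sqrt(35) = 3.35, and noncentral-t power is 90.2%; N = 34 gives 89.3%. So 35 is the smallest N that reaches 90%. Then 35/0.88 = 39.8, rounded up to 40. Both figures reproduce.

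**2. The printed formula.** It carries a factor 2. With sd = 2.5 mm it gives 35. With sd read as the SD of D (3.54 mm) it gives 68. Since 2 × 2.5² = 12.5 = 3.54², the factor 2 belongs with the single-distance SD. This is a slip of notation, and N = 35 stands.

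**3. What four values can show.** The smallest sample SD with extremes 0 and 6 comes from {0, 3, 3, 6}: sqrt(18/3) = 2.45 mm. The largest comes from {0, 0, 6, 6}: sqrt(36/3) = 3.46 mm. The planning value of 3.54 mm lies above both.

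**4. Confidence that the true SD is at most 3.54 mm**, as P(chi-square on 3 df > 3s²/12.5):

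| Sample SD s (mm) | 3s²/12.5 | Confidence |
|---|---|---|
| 2.45 | 1.44 | 69.6% |
| 2.91 (range-based, 6/2.059) | 2.04 | 56.4% |
| 3.46 | 2.88 | 41.0% |

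Using the range directly, which is all the documents report, the figure is the probability that four normal values span more than 6/3.536 = 1.70 SDs: 62.7%.

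**5. Power for a 2 mm shift if the SD is larger.** The one-sided 80% upper limits from step 3's extremes are 4.23 and 5.98 mm.

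| SD of D (mm) | 35 evaluable | 40 evaluable |
|---|---|---|
| 2.5 | 99.6% | 99.9% |
| 3.54 | 90.2% | 93.7% |
| 4.23 | 78% | 83% |
| 5.0 | 63% | 69% |
| 5.98 | 48.5% | 54% |

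Power stays at 90% or more up to an SD of 3.55 mm with 35 cases and 3.80 mm with 40. It stays at 80% or more up to 4.10 and 4.40 mm.

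**6. What an SD check would buy.** Simulated rule: estimate the SD after 20 cases, then reset N between 35 and a cap of 60 evaluable. Power becomes 93% at SD 3.54, 89% at 4.23, 84% at 5.0 and 72% at 5.98 mm, with mean evaluable N of 39, 48, 56 and 59. Type I error is 0.050 to 0.053. Enrolment at the cap is 60/0.88 = 68.2, so 69 instead of 40.

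**The case for a change.** The strongest case for a change is that the plan has almost no margin against a larger SD: 90% power at 35 cases is lost just above 3.54 mm. If the pilot SD is treated as uncertain and power is averaged over that uncertainty, the result is 74 to 88% with 35 cases and 77 to 90% with 40. D needs no follow-up, so an early SD looks feasible, and the simulated rule hardly disturbs the type I error.

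Part of this stands. Conservative cannot mean an upper bound here, and the range of D does not estimate the SDs of x1 and x2. The protocol also refers to the cadaveric femur in the singular. If all four stems went into one specimen, between-patient variation is not in the pilot at all.

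The rest is weaker.

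- The least favourable figures (41% confidence, SD 5.98 mm, 74% average power) require the pilot values to be {0, 0, 6, 6} and then apply normal theory to a two-point pattern.
- The averaged power depends on a chosen distribution for the true SD, one with a long upper tail.
- The larger values of sd_1 are hypothetical, and the pilot's surgeons, instruments and measurement method are not described, so extra spread in patients cannot be demonstrated.
- Under Protocol 6.1.2 the images go for central reading after surgery. No reading deadline is given, and Protocol 11.10 allows 10 working days for sending completed CRFs. With three months of enrolment, the SD from 20 readable pairs could arrive when most cases are already in.
- The rule does not restore 90% power at 5.0 mm, where it gives 84%.

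**Conclusion.** No change is needed. The design delivers the power it states at the SD it assumes. That SD is cautious as a point estimate: 3.54/2.5 = 1.41 times the plan's own value for D, and above the 3.46 mm maximum the pilot range allows. At an SD of 2.5 mm, 19 cases would give 90% power; the plan takes 35. Within the plan's reasoning its claim is also true, because for a fixed sd_1 = sd_2 and a positive correlation, rho = 0 gives the largest SD of D.

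What remains is loose wording and the factor 2 in the formula. Correcting either leaves 35, 40 and every result unchanged. Re-estimating the SD is a fair trade-off that a sponsor may decline: up to 29 more patients (69 - 40) and probably a longer enrolment period, in a post-market observational case series.

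The risk of misreading a non-significant test is handled by ordinary reporting. Protocol section 1 says the study also serves to quantify any difference, and Protocol 9.2 and SAP 7.2 list the mean, SD and 95% interval where appropriate. SAP Table 30 has no interval column, but the interval follows from the same mean, SD and N as the test. With N = 35 and SD 5.0 mm its half-width is 2.032 × 5.0/sqrt(35) = 1.7 mm. An observed mean of 1.0 mm would then give about -0.7 to 2.7 mm, which plainly does not rule out 2 mm.

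These conclusions assume that D is roughly normal, that 0 and 6 mm are the observed pilot extremes, and that the four values are independent. The individual values are not reported, so the true SD of D remains unknown until the study is read.

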9.2. Statistical Analysis

All subjects who meet the study inclusion and exclusion criteria will be included in the statistical analysis. Statistical analyses will be conducted for demographics, pre-operative information, surgical information and safety data. Demographics will include, but not limited to, gender, age, weight, height, BMI. Pre-operative information and surgical information will include any data collected as defined in this protocol. Safety data will

include adverse events, serious adverse event, adverse device effect, serious adverse device effect, unanticipated serious adverse device effect, and device deficiency.

Descriptive statistics for continuous variables will include mean, median, minimum, maximum, standard deviation, and 95% confidence interval, if appropriate. Descriptive statistics for discrete variables will include count and percentage.

Subgroup analyses will be provided if they are necessary. The following sections define the details of primary endpoint and secondary endpoints analyses.

9.2.1. Primary Endpoint Analysis

If the difference between x_1 and x_2 measured from fluoroscopic images approximately follows a normal distribution, then a two-sided paired T test will be used to test the mean. The test statistic is a t-score defined by the following equation:

$$T = \bar{D}/(sd/\sqrt{N})$$

where

$$\begin{aligned}\bar{D} &= N^{-1} \sum_{i=1}^N (x_{i1} - x_{i2}) \\ sd &= \sqrt{\sum_{i=1}^N (x_i - \bar{D})^2 / (N - 1)} \\ x_i &= x_{i1} - x_{i2}, \quad i=1, \dots, N.\end{aligned}$$

The SAS TTEST procedure will be used to perform the paired T test. If the difference does not follow a normal distribution, then the signed rank test will be used to test the hypothesis. The SAS UNIVARIATE procedure will be used to perform the signed rank test.

The null hypothesis will be or not be rejected based on corresponding observed p value from the test above. An alpha value of 0.05 will be used in the hypothesis testing.

9.2.2. Secondary Endpoint Analysis

Descriptive analyses will be presented for the secondary endpoints of leg length discrepancy and intraoperative complications.

9.3. Missing Data

The primary endpoint is an intraoperative measurement so there is no expectation for missing data due to lack of follow up. However, the primary endpoint could be missing due to other issues such as unreadable images. Allowing for 12% missing data, a total sample size of 40 cases is needed in the study.

10. ETHICAL CONSIDERATIONS

10.1. Ethical Approval

In accordance with the Declaration of Helsinki and local regulations of the participating countries, sites must gain written EC approval prior to enrolling research participants in the study.

10.2. Protocol Amendments

Neither the Investigator nor the Sponsor will modify this protocol without mutual agreement. After agreement to initiate the modification - in the form of a protocol amendment - the Investigator agrees not to implement this modification until instructed to do so by the Sponsor. It will be necessary to obtain EC approval prior to implementation of any change in the protocol that may affect the scientific soundness or the rights, safety, or welfare of the subjects involved. Notification shall be submitted to the EC of the study site by the Investigator.

